2.2 Study objective

The purpose of this study was to construct tumor habitat by combining preoperative or postoperative multi-parametric MRI imaging, so as

- (1) to reveal the spatial and/or temporal heterogeneity within tumors;
- (2) to explore the value of habitat imaging in the classification and molecular typing of HGG;
- (3) to investigate the value of parameters quantitatively obtained from habitat in predicting the overall survival time and risk factors of HGG patients;
- (4) to investigate the differential and predictive ability of HGG local recurrence and

intracranial long-distance recurrence;
(5) to verify whether the habitat imaging analysis was more accurate than the traditional holistic tumor analysis in the above studies.

3. Study program

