3.2 Selection criteria

Inclusion Criteria (if we will predict the molecular status and overall survival):

- (1) the patient was over 18 years old;
- (2) the lesion was located in the supratentorial space;
- (3) a histopathologic diagnosis of HGGs according to the WHO CNS4/5;
- (4) all subjects were the first diagnosed cases without any invasive or non-invasive treatment;
- (5) access to the complete preoperative MR imaging examinations, at least including four conventional sequences.

Inclusion Criteria (if we will differentiate recurrence from distant intracranial recurrence):

- (1) the patient was over 18 years old;
- (2) the lesion was located in the supratentorial space;
- (3) a histopathologic diagnosis of HGGs according to the WHO CNS4/5;
- (4) underwent concurrent chemoradiotherapy with temozolomide after surgical resection or biopsy;
- (5) underwent preoperative and postoperative MRI, at least including four conventional sequences;
- (6) had newly appeared or enlarging, measurable, contrast-enhancing mass which raises clinical suspicion of tumor recurrence and distant intracranial recurrence;
- (7) adequate follow-up examinations to determine treatment response on clinic-radiological consensus or pathologic confirmation.

Exclusion Criteria:

- (1) patient with other brain tumors or other grade gliomas at the same time;
- (2) patient with severe basic diseases at the same time;
- (3) patient with a survival time of less than 30 days, which can be caused by severe surgical trauma stress;
- (4) poor image quality and heavy artifact affect the subsequent image processing.

4. Study data and variable collection

- (1) Basic clinical information:
age, sex, height, weight and previous underlying diseases of the patient;
- (2) Image and date collection:
the original MR image and the date of each MRI from preoperative to postoperative to recurrent to follow-up to the last examination, and records tumor location, volume, boundaries, and enhancement patterns;
- (3) Pathological and immunohistochemical data collection:
the specific diagnosis of high-grade glioma and specific molecular characteristics, including IDH, MGMT, TERT, 1p/19q, etc.
- (4) Methods of operation and postoperative treatment:
the extent of resection includes gross total resection, subtotal resection and partial resection, and the adjuvant therapy includes radiation, chemotherapy, chemoradiotherapy, untreated and unknown.
- (5) Prognostic data collection:

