specific overall survival time, recurrence time after treatment, whether there is an endpoint time.
- (6) Quantitative parameter collection:
the corresponding characteristic quantitative parameters were extracted according to different magnetic resonance sequences.

* The data will be collected from the Hospital Information System (HIS), Picture Archiving and Communication System (PACS) and telephone follow-up.

5. Advanced image processing and habitat construction

The multi-parametric MRI images of all patients will be exported from the PACS

system in DICOM format. First of all, all DICOM data will be converted to Nifti format. Subsequently, skull stripping will be performed. Next, the image will be resampled and registered. A deep learning model of nnU-Net will be employed to segment preliminary subregions of enhancing tumor, edema and necrosis on the four conventional structure sequences. Finally, the habitat construction will be carried out using a K-means clustering. Parameter values can be extracted quantitatively from habitats and radiomics features can be extracted quantitatively too.

6. Statistical analysis

Independent-samples T-test or Mann-Whiney U-test will be used to analyze the differences in quantitative parameter values between IDH-mutant HGGs and their wild-type counterpart in each habitat, using Benjamini-Hochberg's procedure for controlling the false discovery rate in multiple comparisons. The Chi-square testing will be used to analyze the constituent ratio of variables. ROC will be applied to evaluate the value of differentiating IDH mutation status and verify the differential efficacy of precise tumor habitats constructed by multi-parametric MRI and traditional tumor habitats. The cutoff values for each habitat were determined by using Youden index. The OS of HGG patients were analyzed using Kaplan-Meier survival analysis and Log-rank test. Specific statistical methods shall be formulated according to specific circumstances

7. Outcomes

Primary outcomes: multi-model habitats constructed by multiparametric MRI predict IDH mutation status and the prognosis in high-grade gliomas (in progress);

Secondary outcomes: multi-model habitats constructed by multiparametric MRI differentiate recurrence from distant intracranial recurrence (in the stage of preparation);

Exploratory outcomes: validate the advantages of habitat imaging and potential links to pathophysiology.

8. Ethical issues

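### Section 6 names only Kaplan-Meier and log-rank for overall survival, with no groups stated and no role for IDH or age, so a positive habitat result would show a marginal association and no more

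*Combined protocol and SAP*

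**What the plan says.** Section 6 gives OS one sentence: "The OS of HGG patients were analyzed using Kaplan-Meier survival analysis and Log-rank test". It closes with a general clause: "Specific statistical methods shall be formulated according to specific circumstances". No regression model, hazard ratio, covariate, stratum or OS grouping variable appears anywhere in the document. Section 6 does mention Youden cutoffs, but these follow the ROC sentence on IDH status and are not tied to OS.

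Four other places bear on what that analysis has to deliver:

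- Section 7, primary outcome: "multi-model habitats constructed by multiparametric MRI predict IDH mutation status and the prognosis in high-grade gliomas".
- Section 2.2, objective (3): "to investigate the value of parameters quantitatively obtained from habitat in predicting the overall survival time and risk factors of HGG patients".
- Section 3.2 sets one list of entry criteria for both aims: "Inclusion Criteria (if we will predict the molecular status and overall survival".
- Section 4 collects "age, sex, height, weight and previous underlying diseases of the patient", then "the specific diagnosis of high-grade glioma and specific molecular characteristics, including IDH, MGMT, TERT, 1p/19q, etc", and under treatment "the extent of resection includes gross total resection, subtotal resection and partial resection", with adjuvant therapy in the same item.

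Section 3.1 describes a single-centre retrospective observational study, so no design feature balances these factors between habitat groups.

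**The concern.** The same habitats, in one cohort, are to predict both IDH status and survival. If IDH affects survival, a habitat that does no more than track IDH will tend to separate the survival curves. The named test cannot tell that situation from one in which the habitat adds prognostic information of its own. Which of the two holds matters for interpretation, because IDH status is itself among the data collected.

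Two further gaps follow from the same sentence. A log-rank test returns a p-value, and Kaplan-Meier returns curves, medians and survival probabilities. Neither returns a hazard ratio or an adjusted estimate, so the risk-factor part of objective (3) has no named method. And because the groups are not stated, the comparison could even be IDH-mutant against wild-type, in which case the habitat would not be tested at all. The closing clause lets groups, covariates and model be settled after the data are seen, for half of a primary outcome.

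**Working it through.** The plan gives no OS figure to reproduce: no sample size, number of deaths, IDH prevalence, AUC or hazard ratio (HR). Every input below is an assumption, and the results show direction and a range only. All tests are two-sided at 0.05.

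**1. Mechanism, by hand.** Assume 35% IDH-mutant, a habitat group with sensitivity and specificity 0.80 for IDH, IDH HR 0.50 (mutant vs wild-type), and no habitat effect once IDH is known.

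- Share in the habitat-positive group: 0.35 × 0.80 + 0.65 × 0.20 = 0.28 + 0.13 = 0.41.
- Mutant share in that group: 0.28 / 0.41 = 68%. In the other group: 0.07 / 0.59 = 12%.
- Average hazard at time zero relative to wild-type: 0.68 × 0.50 + 0.32 × 1 = 0.66, against 0.12 × 0.50 + 0.88 × 1 = 0.94. Ratio 0.66 / 0.94 = 0.70.
- The fitted marginal HR over follow-up is 0.67, although the HR given IDH is 1.
- Schoenfeld power at n=200 (about 145 deaths): √(145 × 0.41 × 0.59) × |ln 0.67| − 1.96 = 5.92 × 0.400 − 1.96 = 0.41, so power is about 66%. Simulation (4,000 runs) gives 60% for the unstratified log-rank and 5% when it is stratified by IDH.

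**2. Range for a continuous habitat parameter.** Assume 25% IDH-mutant, AUC for IDH 0.75-0.85, IDH HR 0.35-0.70, and no habitat effect given IDH. Survival is exponential with wild-type median 15 months, deaths before 1 month are removed to mirror exclusion criterion (3), and censoring is uniform over 12-72 months. There are 2,000 runs per scenario (Monte Carlo SE at most 1.1 points).

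| Analysis | Positive, n=100 | Positive, n=200 |
|---|---|---|
| Log-rank, median split, unadjusted | 7%-36% | 9%-62% |
| Same split, stratified by IDH | 4%-6% | 4%-6% |
| Cox, habitat + IDH | 4%-6% | 4%-6% |

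If IDH has no effect on OS (HR 1.0), the unadjusted test is positive in 5%-6% and the issue disappears. At AUC 0.80 and IDH HR 0.50, moving the prevalence to 10% or 40% gives 8% or 24% at n=100, and 10% or 41% at n=200.

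**3. Why age as well.** Suppose age has HR 1.2-1.4 per SD and correlates 0.4 with the habitat within IDH groups. Cox with IDH but without age is then positive in 9%-18% (n=100) and 14%-33% (n=200). With age it is 4.5%-6.2%. At correlation 0, age is not needed (5%-6% without it). Confounding by MGMT or resection was not simulated.

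**4. Can the data carry the model?** The scenarios in step 2 give 71-77 deaths at n=100 and 142-154 at n=200. For three terms (habitat, IDH, age) that is at least 71 / 3 ≈ 24 and 142 / 3 ≈ 47 deaths per term.

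**5. Power cost of adjusting, like for like.** Assume a real habitat effect of HR 0.80 per SD given IDH, AUC 0.80, IDH HR 0.50, n=100.

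| Form of habitat | Without IDH | With IDH |
|---|---|---|
| Median split, log-rank | about 70% | about 29% |
| Continuous, Cox | about 86% | about 44% |

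Part of each fall is a change of question, because the unadjusted figure includes survival differences carried by IDH. If habitat and IDH are unrelated (AUC 0.50), adjustment costs no power: 30% unadjusted against 32% stratified for the split.

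**The case against.** The strongest reply is that no objective promises value beyond IDH. The comparator the plan names, in objective (5), is conventional whole-tumour analysis. A preoperative marker associated with survival through IDH does answer the primary outcome as worded. This stands. A reader might infer from the rates in the working that the named test has an inflated false-positive rate. It does not: those are correct detections of a real marginal association, and the test is valid for the marginal question.

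A reader might also infer that the plan rules out adjustment, or that the Youden cutoffs for IDH define the survival groups. The text supports neither. The closing clause of Section 6 permits a Cox model, and the absence of adjustment is read from silence. But a clause that names no model, covariate or group pre-specifies nothing.

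The risk-factor wording in objective (3) is ambiguous and need not mean multivariable hazard ratios. Nor is it right to say the plan yields no effect measure, since Kaplan-Meier gives medians and survival probabilities by group. What is missing is a hazard ratio and any adjusted estimate.

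Finally, adjustment costs power and every magnitude is assumed. Both are true. They limit what can be said about size, but not the finding that groups, claim and model are unstated.

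**Conclusion.** The point holds in a limited form and should be fixed. The plan states neither the OS groups nor whether the intended prognostic claim is marginal or independent of IDH, and it pre-specifies no adjusted model although the covariates are on its own collection list. As written, a positive habitat log-rank would support a marginal association at most. It would not support calling habitats independent predictors, and it would not supply adjusted estimates for objective (3). The stronger charge, that the plan promises independent prognostic value and then fails to test it, is not supported by the documents.

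Confidence is high about the omission and low about its size. The direction requires only that IDH affects OS and that the habitat tracks IDH; the magnitudes rest wholly on the assumed prevalence, AUC, hazard ratios and sample sizes.

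**What to change.** In Section 6:

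1. Name in advance the habitat parameter or parameters tested for OS. If there are several, extend the Benjamini-Hochberg procedure to them; at present it is tied to the IDH comparisons. Without this step, an adjusted model still leaves a choice among many parameters.
2. State the Kaplan-Meier and log-rank groups in advance, with cutoffs not chosen on survival, and label the comparison as marginal.
3. Add a pre-specified Cox model with the continuous habitat parameter, IDH and age, reporting hazard ratios with 95% confidence intervals. Add MGMT if the number of deaths and data completeness allow, with a stated rule for missing values. Put extent of resection and adjuvant therapy only in a sensitivity model, because they follow the preoperative MRI.
4. Call habitats independent predictors only on the basis of the adjusted model. If only a marginal claim is meant, say so in Sections 6 and 7.

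The cost is wording and a little more analysis, with no new variables to collect. The habitat effect may look weaker, and power for it falls where habitat and IDH overlap (step 5 of the working). Few deaths would restrict the model to habitat, IDH and age.

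### Log-rank is the only named test for overall survival and no grouping rule or regression model is given, so a quantitative habitat parameter can enter it only after being grouped, usually with loss of information

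*Combined protocol and SAP*

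**What the plan says.** Section 2.2, objective (3), sets the survival question: "to investigate the value of parameters quantitatively obtained from habitat in predicting the overall survival time and risk factors of HGG patients". Section 5 confirms that the predictors are measured on a scale: "Parameter values can be extracted quantitatively from habitats and radiomics features can be extracted quantitatively too". Section 7 places prognosis, next to IDH status, in the primary outcome.

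For OS, section 6 gives one sentence on method: "The OS of HGG patients were analyzed using Kaplan-Meier survival analysis and Log-rank test". It does not name the variable that defines the groups, the number of groups or where they divide. No Cox or other regression model is named anywhere in the document.

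Section 6 has one cutoff rule: "The cutoff values for each habitat were determined by using Youden index". It comes directly after the sentence on ROC analysis for IDH status and before the OS sentence. The section ends with an open clause: "Specific statistical methods shall be formulated according to specific circumstances".

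**The concern.** The predictor in the objective and the test in section 6 do not fit each other. A habitat parameter takes many values, whereas the log-rank test compares groups. To use the named test on such a parameter, someone has to decide how to group it. Grouping treats all patients on one side of a cut as alike and discards the gradient within each side. This loss arises in the unadjusted test itself and is separate from any question of covariate adjustment.

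What is at stake is power for the survival half of the primary outcome. The study is a single-center retrospective cohort with a fixed calendar window (section 3.1), so wider enrolment under the plan cannot make good the lost information. A real prognostic gradient could be missed that the same patients and deaths would have shown.

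**Working it through.** **Inputs from the document.** OS methods: Kaplan-Meier and log-rank (section 6). Predictors: quantitative habitat parameters (sections 2.2 and 5). The document states no sample size, number of deaths, hazard ratio (HR), alpha, power, number of OS groups, split proportion or parameter distribution. There is therefore no figure of the plan's own to reproduce, and everything below rests on assumptions.

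**Step 1. Loss from one cut of a normal parameter.** Assume a log-linear effect on the hazard and a proportion p of patients on one side of the cut. The efficiency of log-rank on the two groups, relative to the Cox score test on the continuous value, is φ(z_p)² / [p(1−p)].

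- Median cut: 0.3989² / 0.25 = 0.637, so 36% is lost.
- 20/80 cut: 0.2800² / 0.16 = 0.490, so 51% is lost.

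The same formula gives losses of 42% at 30/70, 57% at 15/85 and 66% at 10/90.

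**Step 2. Other shapes and more groups.** For any shape, the loss is approximately 1 minus the squared correlation between the parameter and its grouped version.

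- Uniform parameter, median cut: 25%.
- Two normal clusters 3 SD apart, 30% of patients in the upper one, cut between them: 29%.
- Exponential parameter: 35% to 80%, depending on which of the 20th to 80th percentiles is cut.
- Normal parameter in equal-sized groups with a trend test: 21% for three groups, 14% for four, 11% for five.

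**Step 3. What this means in deaths.** Assume two-sided alpha 0.05, 80% power and HR 1.3 or 1.5 per SD.

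- Continuous term: (1.960 + 0.8416)² / (ln HR)². At HR 1.3 this is 7.849 / 0.06883 = 114.03, so 115 deaths.
- Two groups: the log HR between groups is ln HR × φ(z_p)/[p(1−p)], and the number of deaths is 7.849 / [p(1−p) × (group log HR)²]. For a median cut at HR 1.3, the group log HR is 0.2624 × 1.596 = 0.4187, and 7.849 / (0.25 × 0.1753) = 179.1, so 180 deaths.

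| Analysis | Deaths, HR 1.3 per SD | Deaths, HR 1.5 per SD | Power with the continuous-term number of deaths |
|---|---|---|---|
| Continuous | 115 | 48 | 80% |
| Median cut | 180 | 75 | 61% |
| 30/70 cut | 199 | 83 | 57% |
| 20/80 cut | 233 | 98 | 50% |
| 10/90 cut | 334 | 140 | 38% |

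**Step 4. Simulation check.** Assume 150 patients, a normal parameter, exponential survival, random censoring and 4,000 runs. A median cut lost 36%, as in the formula. A 20/80 cut lost 41% with the small group at the high-risk end and 59% to 60% with it at the low-risk end, on either side of the formula's 51%. At HR 1.3 per SD, power was 77% continuous, 57% with a median cut, and 52% or 40% with the two 20/80 cuts. At HR 1.5 per SD it was 98.5%, 90%, and 86% or 75%. The power gap narrows when the effect is strong.

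**The case against.** The strongest reply is that the plan never says it will dichotomise anything. The open clause at the end of section 6 leaves room for a Cox model. The OS sentence names no grouping variable, and log-rank could be meant for natural groups that the plan collects, such as IDH status, extent of resection or adjuvant therapy (sections 4(3) and 4(4)), where nothing is lost. This stands in part: it is wrong to say that the parameters must be cut. But the clause names no method, and if log-rank is meant only for natural groups, objective (3) has no named OS test for its own predictors. Either way the gap remains.

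A reader might infer that the Youden cutoffs will define the OS groups, and that the splits will therefore be very unequal. The documents do not support this. The Youden sentence belongs with the IDH analysis, nothing carries it over to OS, and no split proportion is given.

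It is also fair to say that the calculations favour the continuous test, because they assume a log-linear effect. If risk changed in a step at a known value, grouping at that value could do as well or better. Nor does the point concern validity. In a further simulation of 130 patients with about 99 deaths (both assumed), type I error was 5% to 6% for both the continuous and the split test. The documents set no power target, so no stated target is missed.

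**Conclusion.** The concern holds in conditional form. Section 6 names only Kaplan-Meier and log-rank for OS, with no grouping rule and no regression model, for a question about quantitative parameters that forms part of the primary outcome. The open clause permits a better method but does not commit to one.

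If a roughly normal parameter with a log-linear effect is split in two, the loss is about 36% at the median and 51% at 20/80. It is smaller for a uniform parameter or for several ordered groups with a trend test, and can be larger for skewed parameters. A reader might take a loss of a third to more than half as a property of this plan. It is not: it needs exactly two groups, an assumed shape and, for the upper part, a split of about 20/80 or more unequal. The document states none of these, and every death count, cohort size and HR above is illustrative.

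The weakness is one of efficiency and pre-specification. The sponsor should correct it, but it does not invalidate a log-rank test on groups fixed in advance.

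**What to change.** In section 6, name as the main OS test a Cox model with each habitat parameter as a continuous term, tested by the score or likelihood-ratio test and reported as a hazard ratio per SD with its confidence interval. Specify in advance how non-linearity will be checked, for example a spline with fixed knots, and what will be reported if the check suggests a curve. Keep Kaplan-Meier curves and log-rank on groups as descriptive or supportive, and state the grouping rule for them (for example tertiles) before the survival data are examined. If log-rank is also meant for natural groups such as IDH status, say so.

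The cost is SAP wording only, with no new data or patients. The downside is the log-linearity assumption. With few deaths a spline check has limited power, so it covers that assumption only in part. Choosing the model from the result of the check would make the analysis data-dependent, which is why the rule should be fixed beforehand.
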